APPENDIX D

Karnofsky Performance Status Criteria

Able to carry on normal activity; no special care is needed

100	Normal; no complaints; no evidence of disease	(ECOG 0)
90	Able to carry on normal activity	(ECOG 0)
80	Normal activity with effort	(ECOG 1)

Unable to work; able to live at home, cares for most personal needs; a varying amount of assistance is needed

70	Cares for self; unable to carry on normal activity or to do active work	(ECOG 1)
60	Requires occasional assistance but is able to care for most needs	(ECOG 2)
50	Requires considerable assistance and frequent medical care	(ECOG 2)

Unable to care for self; requires equivalent of institutional or hospital care; disease may be progressing rapidly

40	Disabled; requires special care and assistance	(ECOG 3)
30	Severely disabled; hospitalization indicated, although death not imminent	(ECOG 3)
20	Very sick; hospitalization necessary	(ECOG 4)
10	Moribund; fatal process progressing rapidly	(ECOG 4)

APPENDIX E. Comorbid Conditions

Comorbidity score per Sorrow, et al.

Comorbidity	Definitions of comorbidities included in the new HCT-CI	HCT-CI weighted scores
Arrhythmia	Atrial fibrillation or flutter, sick sinus syndrome, or ventricular arrhythmias	1
Cardiac‡	Coronary artery disease,§ congestive heart failure, myocardial infarction, or EF ≤ 50%	1
Inflammatory bowel disease	Crohn disease or ulcerative colitis	1
Diabetes	Requiring treatment with insulin or oral hypoglycemics but not diet alone	1
Cerebrovascular disease	Transient ischemic attack or cerebrovascular accident	1
Psychiatric disturbance†	Depression or anxiety requiring psychiatric consult or treatment	1
Hepatic, mild‡	Chronic hepatitis, bilirubin > ULN to 1.5 × ULN, or AST/ALT > ULN to 2.5 × ULN	1
Obesity†	Patients with a body mass index > 35 kg/m ²	1
Infection‡	Requiring continuation of antimicrobial treatment after day 0	1
Rheumatologic	SLE, RA, polymyositis, mixed CTD, or polymyalgia rheumatica	2
Peptic ulcer	Requiring treatment	2
Moderate/severe renal‡	Serum creatinine > 2 mg/dL, on dialysis, or prior renal transplantation	2
Moderate pulmonary‡	Dlco and/or FEV ₁ 66%-90% or dyspnea on slight activity	2
Prior solid tumor‡	Treated at any time point in the patient's past history, excluding nonmelanoma skin cancer	3
Heart valve disease	Except mitral valve prolapse	3
Severe pulmonary‡	Dlco and/or FEV ₁ ≤ 65% or dyspnea at rest or requiring oxygen	3
Moderate/severe hepatic‡	Liver cirrhosis, bilirubin > 1.5 × ULN, or AST/ALT > 2.5 × ULN	3

*composite score obtained by summing total points

*modification made to “pulmonary” co-morbidity: given marked discrepancy in frequency distribution of reduced DLCO in analysis of 59 contemporary patients from our center compared to published standards, decrement in DLCO alone will not factor into calculation of “pulmonary” comorbidity. Only those with DLCO < 50% will be considered to have “severe pulmonary” comorbidity and be excluded from the trial.

*psychiatric disturbance: only those with psychiatric disturbance (such as depression and/or anxiety) requiring therapy or treatment will be assigned a point on this measure.

Non-relapse mortality per Sorrow, et al

Score	Training set			Validation set		
	Patients, %	NRM		Patients, %	NRM	
		HR* (95% CI)	2-year, %		HR* (95% CI)	2-year, %
0	38	1	9	38	1	14
1	17	1.66 (0.9-3.1)	14	18	1.57 (0.7-3.3)	22
2	17	3.48 (2.0-6.0)	27	17	1.26 (0.6-2.8)	19
3	17	6.09 (3.7-10.1)	41	15	3.95 (2.1-7.5)	41
4 or more	11	6.93 (4.0-12.0)	43	13	3.05 (1.5-6.2)	40

APPENDIX F

Translational research Introduction:

The goals of correlative studies are to test the pharmacodynamics of PANO administered in for GVHD prevention. We will determine whether PANO abrogates HCT induced cytokine storm, if there is a correlation between HDAC enzymatic activity inhibition and clinical GVHD prevention; we will establish whether there is enhanced proteins/histones acetylation in T-cell subsets that may be responsible for GVHD prevention and effects on immune reconstitution. Samples will be collected with the AM blood draw whenever possible. Samples will be labeled with the patient's name and Moffitt unique patient number (UPN), date and time of draw, and transported immediately by courier to the Moffitt Cancer Center Research laboratory no. 22324, in the Stabile Building at the Moffitt Cancer Center and/or to Novartis pharmaceutical (If PK performed. Samples acquisition, results and statistics will be recorded into a Microsoft Excel database.

Data for each correlative study performed from the whole study population (patients receiving TAC+SIR +PANO) will be presented over time and compared to data from similar “external control” patients treated TAC/SIR with identical inclusion and exclusion criteria except that will not be treated with PANO. We are going to accrue **n=20** subjects as “external control”. These patients will be consented with an specific “external control” consent.

Immune Reconstitution after TAC/SIR/PANO:

To describe the kinetics of total T cells, CD4+ (T helper) and CD8+ (T cytotoxic), Th1, Th2, Th17, regulatory T-cells (Tregs), CD19+ (B cells), CD56 (NK cells) and DCs cell subsets recovery following TAC/MTX/PANO treatment FACS analysis will be performed on lysed whole blood samples with previously established multicolor antibodies panels. FACS Calibur flow cytometer will be used for acquisition and analysis will be performed with FlowJo software. All appropriate compensation tubes, including fluorescence minus 1, will be prepared from normal donor blood cells. The absolute lymphocyte subset counts will be determined using the formula: (absolute subset count) x (percentage of events positive for the TEST). To test circulating monocytes and/or DCs we will establish a lineage negative (Lin-) panel consisting of CD3, CD19, CD16, 14 and CD56 antibodies. Monocytes will be characterized by CD14+, 16+ (or CD16-), CD11c-, CD86- and CD123 low/neg cells. Dendritic cells subsets will be gated on the Lin- and HLA-DR+ gate. Monocytes derived DCs (CD11c+, CD86+, CD123-), plasmacytoid DC (CD11c-, CD86+, CD123++) and 6-sulfoLacNac DC (sIaDC) (M-DC8+/1c-/11c+14- 16+ 45RA+ 5aR+).

In addition we will test for type-2 myeloid dendritic cells by BDCA-3 (CD141) expression. Absolute cell counts will be enumerated using the Becton Dickinson TruCOUNT tubes with MultiSET software. Flow cytometry and absolute cell counts will be enumerated before PANO administration (days -30 to -5, 15(+/-3), 28(+/-3), 90(+/-14) and 365(+/-45) in order to determine changes in the absolute cell numbers over time. In a group of patients we will correlate the flow cytometry findings with Western blot acetylation analysis of PBMC at the same time points. Data for each cell subset from the whole study population will be presented over time and compared to data from similar external control patients treated TAC/SIR with identical inclusion and exclusion criteria except that will not be treated with PANO.

-

Histone acetylation of T cells and DC subsets with TAC/SIR/PANO

To determine the level of protein acetylation and more specifically of hyper-acetylated histones (H3 and/or H4) in total T cells, T-regs, CD4/CD8 and DC subsets in peripheral blood we will use multi parameter flow cytometry assay. In a group of patients we will correlate the flow cytometry results by histone acetylation measured by Western blot analysis of PBMC. We speculate that TAC/SIR/PANO will lead to an overall increase in the number of acetylated proteins. It remains to be determined which T-cell subsets will be more susceptible to HDACi with PANO at this point. In summary, whole blood will be collected and separated in 100 μ L aliquot and/or PBMC (5-10x10⁶) will be obtained after Ficoll-Paque or Buffy coat/RBC lysis separation. For multiparameter flow staining, an aliquot containing at least 1 x 10⁶ cells will be used per tube if possible. Cells will be washed in PBS and fixed with 0.4% paraformaldehyde in PBS for 5-10 minutes at 37°C and washed with buffer. The fixed cells will be re-suspended in permeabilization buffer for 5 minutes (0.4% Triton X-100 in wash buffer) and then washed. After fixation and permeabilization, cells will be stained with anti-acetylated-lysine or anti-acetylated histone antibodies as well as with a variety of lymphocytes markers (CD4, CD8, CD3, CD25 and/or CD117) and apoptosis detection markers including annexin, 7-AAD and/or caspase 3. Some antibodies may be directly labeled with fluorochrome prior to their use to minimize secondary antibody staining background. All compensation tubes, including fluorescence minus 1, will be prepared from normal donor blood cells. Test will be done before PANO administration on day -5, and on days 30 to -5, 15(+/-3), 28(+/-3), 90(+/-14) and 365(+/-45). Data for histone acetylation and DC subset from the whole study population will be presented over time and compared to data from similar external control patients treated TAC/SIR with identical inclusion and exclusion criteria except that will not be treated with PANO.

T reg immune-reconstitution, Foxp3⁺ expression and acetylation with TAC/SIR/PANO

T-regs will be measured with the 259D Biosciences Biolegend Foxp3 kit antibody that identifies CD4⁺CD25⁺ Tregs and/or by FACS as determined by the lack of CD127 expression. Since Foxp3 requires cell membrane permeabilization, standard viable dyes are not applicable. The Live/Dead Fixable Dead Cell Violet Stain (L/D) from Molecular Probes will be used for exclusion of dead cells. We propose that one of the benefit conferred by TAC/SIR/PANO-based immune suppression results from apoptosis of alloreactive donor non-Treg CD4⁺ cells while sparing T regulatory cells that mitigate GVHD risk and promote immune tolerance. Accordingly, we will study the proportion of Treg/total CD4⁺ cells. We will also measure the expression of *FOXP3* and *IDO* mRNA in PBMC by RT-PCR. Test will be done before PANO administration on day -30 to -5, and on days 30 to -5, 15(+/-3), 28(+/-3), 90(+/-14) and 365(+/-45). Data for T-reg immune reconstitution and acetylation from the whole study population will be presented over time and compared to data from similar external control patients treated TAC/SIR with identical inclusion and exclusion criteria except that will not be treated with PANO.

Inflammatory cytokine expression profiling with TAC/SIR/PANO

In order to rapidly and accurately measure the expression levels of up to 40 cytokines/chemokines and other relevant proteins in GVHD inflammation (cytokine storm) we will use a human inflammation antibody array assay. The technology is designed based on the sandwich immunoassay principle. A panel of antibodies (capture) is immobilized in the specific spot locations on the surface of membrane. Incubation of array membranes with biological samples results in capturing cytokines by corresponding antibodies. The bound cytokines are detected with a cocktail of biotinylated antibodies. Signals are then visualized using chemiluminescence. We hypothesize that HDACi will reduce the level of expression of pro-inflammatory cytokines like TNF/IFN and increase level of tolerogenic cytokines (TGFb-b /IL-10). We will use a Raybiotech's Human inflammation antibody array (catalog #, AAH-INF -3-8) to detect the following cytokines IL-1, 2, 3, 4, , 6, 7, 8, 10, 11, 12, 13, 15, 16, 17 , IFN, TNF- α , TNF- β , TNF RI, s TNF RII, MCP1-2, M-CSF, MIP, GM-CSF, G-CSF among others proteins.

We will also measure serum levels of soluble IL-2 receptor α using a commercially available ELISA kit. Test will be done before PANO administration on day 30 to -5, 15(+/-3) and 28(+/-3). Data for inflammatory cytokines from the whole study population will be presented over time and compared to data from similar external control patients

treated TAC/SIR with identical inclusion and exclusion criteria except that will not be treated with PANO.

GVHD Biomarkers

ELISA-based analysis will be used to determine whether a marker panel comprised of IL-2R α , TNFR1, HGF, IL-8, Elafin, REG-3 α and ST2 levels tested prospectively at 30 to -5, and 15(+/-3) after allogeneic HCT is able to predict for the development of acute GVHD. Test will be done before PANO administration on day -30 to 5, and on days 15+/-1. Data for GVHD biomarkers from the whole study population will be presented over time and compared to data from similar external control patients treated TAC/SIR with identical inclusion and exclusion criteria except that will not be treated with PANO.

Stat-3 activation and acetylation, STAT-5 and S6 phosphorylation

To determine the functional impact of HDACi on PBMCs we will measure total STAT-3, phosphorylated STAT3 and acetylated STAT-3 by WB and flow cytometry in PBMC and gated T/DCs cells populations in patients and external controls on day 30 to -5, 15(+/-3), 28(+/-3), 90(+/-14) and 365(+/-45). T-cell STAT5 and S6 phosphorylation will also be measured among the external controls on day +30+/-3 and day +90+/-314. Data for stat-3/stat-5 and S6 phosphorylation and/or acetylation subset from the whole study population will be presented over time and compared to data from similar external control patients treated TAC/SIR with identical inclusion and exclusion criteria except that will not be treated with PANO.

Note: The data gathered on these results will be used for future analysis not considered in the context of this proposal. Thus, after identifying changes in phenotype and the expression pattern of immune-related genes upon PANO/TAC/SIR treatment, we will expand our research to investigate the role of PANO in their regulation.

List of Test to be performed in patients treated with TAC+SIR+PANO and “external control patients” treated with TAC+SIR only:

TEST	-30 to -5	15(+/-3)	28(+/-3)	90(+/-14)	365(+/-45)
ImmuneReconstitution (T, DCs and Tregs)	x	x	x	x	x
Histone Acetylation (T and DCs)	x	x	x	x	x
STAT-3 activation and acetylation	x	x	x	x	x
Cytokine profiling	x	x	x		
Biomarker profiling	x	x			

*Note: T-cell STAT5 and S6 phosphorylation will also be measured among the external controls on day +28 (+/- 3) and day +90(+/-10).

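### Appendix F defines one dendritic cell subset as CD16-positive but gates it where CD16-positive cells have been removed; the acetylation marker list also needs aligning with the rest of the appendix

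*Combined protocol and SAP*

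**What the plan says.** Appendix F, Immune Reconstitution after TAC/SIR/PANO, describes the flow cytometry for circulating monocytes and DCs. The lineage panel is given as "we will establish a lineage negative (Lin-) panel consisting of CD3, CD19, CD16, 14 and CD56 antibodies". The parent gate follows: "Dendritic cells subsets will be gated on the Lin- and HLA-DR+ gate". The subsets named are monocyte-derived DCs, plasmacytoid DCs and "6-sulfoLacNac DC (sIaDC) (M-DC8+/1c-/11c+14- 16+ 45RA+ 5aR"+), with CD141-positive type-2 myeloid DCs added afterwards. Monocytes have their own phenotype and no stated parent gate: "Monocytes will be characterized by CD14+, 16+ (or CD16-), CD11c-, CD86- and CD123 low/neg cells".

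The next part of Appendix F, on histone acetylation, says that acetylation will be measured "in total T cells, T-regs, CD4/CD8 and DC subsets in peripheral blood we will use multi parameter flow cytometry assay". The lymphocyte markers it lists are "CD4, CD8, CD3, CD25 and/or CD117". The Treg part that follows identifies Tregs by a Foxp3 kit antibody (CD4+CD25+) and/or by flow cytometry "as determined by the lack of CD127 expression".

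The objectives table in Section 2.2 places these studies under secondary exploratory objectives. Section 12.5 also treats the secondary analyses as exploratory, and it compares T-cell and DC profiles with the external control by the Satterthwaite t-test.

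**The concern.** A cell that must be CD16-positive cannot lie inside a gate from which CD16-positive cells have been removed. The text gives no exception and no separate gate for the 6-sulfoLacNac DC. A laboratory following it literally would find none in either group, and a t-test on values that are all zero has no defined result. If a few dimly stained cells passed the gate, the count would reflect gate leakage and not DC recovery.

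The acetylation list matters for a related reason. The Treg part of Appendix F expects the regimen to kill alloreactive non-Treg CD4 cells while sparing Tregs. Section 1.1 reports that under sirolimus Treg numbers rose and non-Treg CD4 numbers fell. A CD4+CD25+ gate without Foxp3 or CD127 may mix the two populations and blur the contrast that the assay is meant to show.

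**Working it through.** The only figures attached to these comparisons are the two power statements in Section 12.5, so those were reproduced first. For a two-sample t-test, two-sided at 5%, with n per group and effect size d, the noncentrality is d × √(n/2) on 2n − 2 degrees of freedom.

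- 15 per group, d = 1.1: 1.1 × √7.5 = 3.01 on 28 df. Power is 82.8%; the plan states 83%.
- 20 per group, d = 1.0: 1.0 × √10 = 3.16 on 38 df. Power is 86.9%; the plan states 87%.

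Both reproduce, and neither depends on the gating.

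The gate itself is a matter of set logic. Let L be the markers that a lineage-negative cell must lack: CD3, CD19, CD16, CD14 and CD56. A subset whose required positive markers include any member of L is empty inside the gate.

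| DC subset | Required positive markers | Shared with L |
|---|---|---|
| Monocyte-derived | CD11c, CD86 | none |
| Plasmacytoid | CD86, CD123 | none |
| Type-2 myeloid | CD141 | none |
| 6-sulfoLacNac | M-DC8, CD11c, CD16, CD45RA, C5aR | CD16 |

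One of the four named subsets conflicts with the gate, through CD16 alone. Its CD14-negative requirement is compatible. Monocytes are CD14-positive and would also be lost inside a lineage-negative gate, but the text applies that gate only to DC subsets, so no conflict arises for them.

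The test table at the end of Appendix F schedules immune reconstitution at five times (days −30 to −5, 15, 28, 90 and 365) in treated patients and external controls alike. The conflict applies to every one of those samples.

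For the acetylation assay, compare three lists in Appendix F:

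- Listed in the acetylation part: CD3, CD4, CD8, CD25 and/or CD117.
- Used in the Treg part: CD4 and CD25 with Foxp3, and/or absence of CD127.
- Used in the immune reconstitution part for DCs: HLA-DR, CD11c, CD86, CD123, M-DC8 and CD141.

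The first list contains CD4 and CD25. It contains neither Foxp3 nor CD127, and none of the DC markers. CD117 occurs only here. CD127 is used for Tregs in the Treg part and in the earlier panobinostat maintenance study summarised in Section 1.4.

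**The case against.** The strongest reply on the gate is that the same antibodies are introduced for monocytes as well as DCs, and monocytes are then identified by CD14 and CD16 positivity. The panel therefore also serves for positive identification. The 6-sulfoLacNac DC has its own explicit phenotype, and an experienced laboratory might gate on that and disregard the parent gate. This bears on likely practice, but it does not remove the contradiction: the parent gate is stated for DC subsets without exception. What stands is that an empty subset is the result of the written rule and not a forecast of the laboratory's data. A reader might also infer that zeros in both groups would be reported as no treatment difference. Nothing in the documents says that a uniformly empty subset would be analysed or reported in that way.

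On the acetylation list the reply carries more weight. A reader might infer that acetylation in Tregs and DCs cannot be measured at all, or that objective 2.2.2.3 fails. The documents do not support either. The list is part of a summary, is presented as a selection of lymphocyte markers, and ends in and/or, so it need not be the full panel. CD4 and CD25 are on it. Objective 2.2.2.3 has its own part of Appendix F with the Foxp3 and/or CD127 route. What remains is that this list is the only marker specification given for the acetylation assay, and it does not match the parts on either side of it.

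On importance, the 6-sulfoLacNac DC is not named in the Section 2.2 objectives or in the closing test table, and the work is labelled exploratory. That is correct and makes this a low-priority correction.

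**Conclusion.** The first point holds: the DC gating is wrong as written for one of four named DC subsets, at all five sampling times and in both groups. It rests on reading the lineage-negative gate literally, with CD16-positive cells excluded, and on the printed plus and minus signs being as intended.

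The second point is a specification gap and not a demonstrated failure. The acetylation list carries an unexplained CD117, omits both markers that the Treg part uses to separate Tregs from other CD4+CD25+ cells, and names no DC marker. That CD117 stands in place of CD127 is the likeliest explanation, but the documents do not confirm it.

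Both points are confined to exploratory correlative assays. The primary endpoint, sample size, stopping rules and stated correlative power (83% and 87%) are unaffected, and no figure in the plan changes.

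**What to change.** In the immune reconstitution part of Appendix F, give the 6-sulfoLacNac DC its own gate before the CD16 exclusion: HLA-DR+ CD14− M-DC8+ CD11c+ CD16+. Keep the lineage-negative, HLA-DR-positive gate for the other DC subsets. This is preferable to dropping CD16 from the lineage panel, which would also change the gate for three subsets that have no conflict. State that CD16 is to be read separately from the other lineage markers, since the new gate depends on it.

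In the acetylation part, check CD117 against CD127 and correct it if it is a slip. Name Foxp3 and/or CD127 for Tregs and the DC markers already used in the immune reconstitution part, or state that the list is illustrative and refer to the full panel.

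The first change is a wording amendment using markers already named. The second is wording plus reagents already named in the appendix. The acetylation protocol already permeabilises cells, as Foxp3 staining requires. Whether the added markers fit the available cells and tubes is for the laboratory to confirm: the documents give 100 µL aliquots and/or 5–10 × 10⁶ mononuclear cells, with at least 1 × 10⁶ per tube if possible, but no tube count or colour capacity. The change is best made before samples are run, because baseline samples might not be recoverable later.

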Appendix G.

Panobinostat administration as per conditioning regimen. Patients will be treated with PANO 5 MG PO TIW (3 doses about 48 hours apart in a 7 day period) QW for 26 weeks starting prior to stem cell infusion. During the study, PANO will be administered orally as once daily dose. Patients should receive their once-a-day oral dose of PANO approximately at the same time each day in AM. Each dose of PANO should be taken with about 8 oz / 240 ml glass of water. Patients should be instructed to swallow the capsules whole and not chew them. Patients must avoid grapefruit or grapefruit juice and seville (sour) oranges during the entire study. If the patient forgets to take his/her dose on scheduled treatment day or cannot take it due to mucositis and/or HCT related GI toxicities (nausea/vomit), then he/she should take PANO on that same day within 16 hours after the missed dose if possible. After more than 16 hours, that day's dose should be withheld, and the patient should wait to take PANO until the next scheduled treatment day (i.e., patients should be instructed not to try to make-up the missed dose after 16 hours). If mucositis and/or GI toxicity preclude PANO oral intake, patient are allowed to hold up to 3 doses and administration should be resumed once mucositis and/or toxicity resolves. Patient should complete missed doses and then continue treatment as planned per protocol extending PANO administration period.

Busulfan and Fludarabine Chemotherapy

Sunday	Monday	Tuesday	Wed	Thursday	Friday	Saturday
-5 BU FLU PANO(1)	-4 BU FLU	-3 BU FLU PANO(2)	-2 BU FLU	-1 PANO(3)	0	+1
+2	+3 PANO	+4	+6 PANO	+7	+8 PANO	

Sunday	Monday	Tuesday	Wed	Thursday	Friday	Saturday
			-6 BU FLU PANO(1)	-5 BU FLU	-4 BU FLU PANO(2)	-3 BU FLU
-2 PANO(3)	-1	0	+1 PANO	+2	+3 PANO	+4
+5	+6 PANO	+7	+8 PANO		+10 PANO	

Fludarabine and Melphalan Chemotherapy

Sunday	Monday	Tuesday	Wed	Thursday	Friday	Saturday
			-5 FLU/MEL PANO	-4 FLU/MEL	-3 FLU/MEL PANO	-2 FLU/MEL
-1 Rest PANO	0	+1	+2 PANO	+3	+4 PANO	+5
+6	+7 PANO	+8	+9 PANO	+10	+11 PANO	+12
Sunday	Monday	Tuesday	Wed	Thursday	Friday	Saturday
				-5 FLU/MEL PANO	-4 FLU/MEL	-3 FLU/MEL PANO
-2 FLU/MEL	-1 Rest PANO	0	+1	+2	+3 PANO	+4
+5	+6 PANO	+7	+8 PANO	+9	+10 PANO	+11
Sunday	Monday	Tuesday	Wed	Thursday	Friday	Saturday
					-5 FLU/MEL PANO	-4 FLU/MEL
-3 FLU/MEL PANO	-2 FLU/MEL	-1 Rest PANO	0	+1	+2 PANO	+3
+4	+5 PANO	+6	+7 PANO	+8	+9 PANO	+10

Fludarabine and Melphalan Chemotherapy

Sunday	Monday	Tuesday	Wed	Thursday	Friday	Saturday
						-5 FLU/MEL PANO
-4 FLU/MEL	-3 FLU/MEL PANO	-2 FLU/MEL	-1 Rest PANO	0	+1	+2
+3 PANO	+4	+5	+6 PANO	+7	+8 PANO	+9
+10	+11 PANO	+12	+13 PANO		+15 PANO	

Sunday	Monday	Tuesday	Wed	Thursday	Friday	Saturday
5 FLU/MEL PANO	-4 FLU/MEL	-3 FLU/MEL PANO	-2 FLU/MEL	-1 Rest PANO	0	+1
+2	+3 PANO	+4	+5 PANO	+6	+7 PANO	+8
+9	+10 PANO	+11	+12 PANO	+13	+14 PANO	+15

Busulfan and Fludarabine Chemotherapy

Sunday	Monday	Tuesday	Wed	Thursday	Friday	Saturday
-5 BU FLU PANO(1)	-4 BU FLU	-3 BU FLU PANO(2)	-2 BU FLU	-1 PANO(3)	0	+1
+2	+3 PANO	+4	+6 PANO	+7	+8 PANO	

Sunday	Monday	Tuesday	Wed	Thursday	Friday	Saturday
			-6 BU FLU PANO(1)	-5 BU FLU	-4 BU FLU PANO(2)	-3 BU FLU
-2 PANO(3)	-1	0	+1 PANO	+2	+3 PANO	+4
+5	+6 PANO	+7	+8 PANO		+10 PANO
